# CSPOT (Conduction System Pacing Optimized
Therapy) Clinical Investigation PlanFormVersion 4.0, 29-Apr-2022Page 36 of 88Medtronic

Pacing leads (and defibrillation lead for CRT-D) will then be positioned as described in the CSPOT User Manual. Finally, a Millar pressure catheter will be introduced via the femoral artery retrograde across the aortic valve into the LV for hemodynamic pressure monitoring.

The different pacing configurations are depicted below and include univentricular (LVcs) pacing (CRT-P implants only), LVcs and RV pacing (CRT-D implants only), univentricular CSP (LBBP), and conduction system pacing optimized therapy (CSPOT) which is dual LV pacing of best LVcs and CSP. Different atrioventricular (AV) and intra-ventricular VV intervals will be evaluated. See figure 3 below for an overview.

[figure not shown]
[figure not shown]

Figure 3: Pacing Configurations

Version 4.0, 29-Apr-2022

Page 38 of 88

Form

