# 11. Risks and Benefits

# 11.1 Potential Risks

Medtronic follows rigorous Quality Assurance and Control procedures throughout the life of a product, from the business analysis phase through development, market release, and post-market surveillance. The risk analysis process for the CSPOT Research System is being performed in accordance with ISO 14971:2019 and ensures that the level of risk is acceptable prior to starting the study. In Europe a summary of the risk analysis and risk assessment will be listed in the IB.

The potential risks to a subject participating in this study are believed to be somewhat higher than those encountered during standard CRT (CRT-P and/or CRT-D) implantation. This is due to 1) the prolonged duration of the complete procedure, 2) the insertion of the Millar catheter in the left ventricle, and 3) in CRT-D devices, the addition of the CSP lead for LBBP. The potential adverse events are outlined below:

- Allergic reaction
- AV fistula
- Bradyarrhythmia
- Cardiac arrest
- Cardiac inflammation
- Cardiac perforation
- Cardiac tamponade
- Cardiac valve damage
- Discomfort
- Dizziness
- Dyspnea
- Embolism
- Fever
- Groin site injury
- Hematoma
- Hemorrhage
- Hiccups
- Hospitalization
- Infection
- Lethargy
- Mental anguish
- Palpitations
- Pneumothorax
- Physical injury

Version 4.0, 29-Apr-2022

Page 47 of 88

Medtronic

- Return of cardiac symptoms
- Skeletal muscle sensation or twitching
- Skin disorders
- SVC tear
- Syncope
- Tachyarrhythmia
- Threshold elevation
- Tissue trauma
- Vessel perforation

Kidney dysfunction could be another risk because of increased use of contrast fluid used during the total study protocol.

Bleeding and bruising may be more likely to occur with the administration of blood-thinning medications (heparin) to minimize the risk of blood clot formation during the procedure.

Procedure prolongation will not only increase duration of the anesthesia but also the risk of infection. The protocol procedures may take up to 90 minutes longer than the standard CRT procedure time which includes up to 10 minutes of fluoroscopy exposure.

Placement of the 3830 lead to pace the left bundle branch could result in: temporary or permanent right bundle branch block, tricuspid valve damage, or perforation of the ventricular septum.

Additional potential risks associated with the CSPOT Research System to a subject participating in this study are:

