### 12. Adverse Events and Device Deficiencies

### 12.1 Adverse Events

AE definitions are provided in Table 10. To comply with ISO 14155:2020, all adverse events (AEs) will be collected throughout the duration of a subject's participation in the study and reported per the study protocol. In addition, AEs impacting users or other persons, Non-subject Adverse Events will be collected. In all geographies, Unavoidable AEs, listed in Table 10, need not be reported unless the adverse event worsens or is present outside the stated timeframe post-implant.

For AEs that require immediate reporting initial reporting may be done by phone, fax, or on the eCRF completing as much information as possible. The completed AE eCRF must be submitted to Medtronic as soon as possible.

Any medication/treatment associated with the treatment of an AE must be reported.

Subject deaths are also required to be reported. Refer to Section 12.6 for Subject Death collection and reporting requirements.

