Serious Health Threat	Signal from any adverse event or device deficiency that indicates an imminent ri death or a serious deterioration in the h subjects, users or other persons, and th requires prompt remedial action for oth subjects, users or other persons	sk of ealth in nat
	NOTE 1: This would include events that a significant and unexpected nature such the become alarming as a potential serious he hazard or possibility of multiple deaths of at short intervals.	hat they ealth
	(ISO 14155:2020, 3.46)	
	Other	
Non-Subject Adverse Event (users or other persons) Unavoidable Adverse Event	An Adverse Event or Serious Health The investigational medical devices or comp impact users or other persons An Adverse Event inherent to a surgica expected to occur in all subjects for a p according to the Investigator's opinion limited to:	parators that Il procedure that is projected duration
	Event Description	Timeframe (hours) from the Surgical Procedure
	Anesthesia related nausea / vomiting	24
	Low-grade fever (<100°F or 37.8°C)	48
	Pocket site / Incisional pain	72
	Mild to moderate bruising / ecchymosis	168
	Sleep problems (insomnia)	72
	Back pain related to laying on table Shoulder pain/discomfort/stiffness	72
	related to shoulder immobilization during procedure	72
	Unavoidable adverse events are not reportab worsens or is present outside the stated time	

Version 4.0, 29-Apr-2022 Pa

Page 57 of 88

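### The unavoidable-event list exempts early mild to moderate bruising with no site limit, so femoral bruising from the research catheter need not be reported

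*Protocol*

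**What the plan says.** Protocol Table 10 (Section 12.4) defines an unavoidable adverse event as one that belongs to a surgical procedure and is expected in every subject for a limited time, in the investigator's opinion. It then lists events with windows in hours from the procedure. One line is "Mild to moderate bruising / ecchymosis", with a window of 168 hours. The pain line, by contrast, is tied to the pocket site or incision (72 hours).

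Section 12.1 gives the reporting rule for all geographies: "Unavoidable AEs, listed in Table 10, need not be reported unless the adverse event worsens or is present outside the stated timeframe". Section 12.5.1.1 repeats it.

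Section 10.6.1 describes the added catheter step: "a Millar pressure catheter will be introduced via the femoral artery retrograde across the aortic valve into the LV". Section 11.1 names the insertion of this catheter as one of three reasons why risk is somewhat higher than in standard CRT implantation. It also says: "Bleeding and bruising may be more likely to occur with the administration of blood-thinning medications (heparin").

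SAP 7.10 refers to Section 12 of the protocol, says that all adverse events will be collected from consent, and plans counts of events and subjects with system- or procedure-related events. It does not mention the unavoidable-event exemption.

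**The concern.** The exemption is meant for the ordinary, expected after-effects of implant surgery. In this study the procedure also contains a research step with its own arterial access site, away from the device pocket. The bruising line does not distinguish the two. A bruise in the groin that would not exist without the research catheter is treated like a bruise over the pocket.

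At stake is the completeness of the safety description. The synopsis says the safety of the system will be assessed, and Section 11.3 says subjects may gain no direct benefit. The minor burden of research-only steps is therefore part of the risk-benefit account, and this piece of it would be left out.

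**Working it through.** No stated figure is in dispute and the documents give no event rates, so the check is a comparison of texts.

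1. **Is the femoral puncture added by the study?** Section 10.6.1 places it in the acute pacing protocol, for hemodynamic monitoring. Section 11.1 lists catheter insertion among the reasons for risk above standard CRT implantation. The documents describe no femoral arterial access for the routine implant. I take the puncture to be research-only on that basis.

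2. **Does the exemption reach that site?** The bruising line has a severity limit (mild to moderate) and a time limit (168 h; 168 / 24 = 7 days, the longest window in the table). It has no limit by site or cause. Other lines do: pain is tied to the pocket or incision, back pain to the table, shoulder pain to immobilization. On its wording, the bruising line covers the groin.

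3. **What stays reportable?** Severe bruising, bruising that worsens, and bruising still present after 168 h. Section 11.1 also lists hematoma, hemorrhage, groin site injury, AV fistula and vessel perforation as potential adverse events, and none is on the exempt list. What is lost is mild to moderate femoral bruising that does not worsen and clears within 7 days.

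4. **Would anything else record it?** Table 6 and the visit lists in Sections 10.6 and 10.7.1 name no access-site check. Section 10.7 schedules no visit between implant and the 6-month visit (window 150 to 210 days). A bruise gone within a week depends on adverse event reporting.

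5. **Where would it have appeared?** Table 5 lists the pressure catheter as a component of the research system. SAP 7.10 plans to give, for system-related events, the component involved, and to tabulate by MedDRA Preferred Term. A reported femoral bruise would show in those tables without any new table.

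6. **Do the other lines raise the same problem?** Section 11.1 says "Procedure prolongation will not only increase duration of the anesthesia but also the risk of infection", and the procedure may take up to 90 minutes longer. Table 10 exempts "Anesthesia related nausea / vomiting" (24 h), "Back pain related to laying on table" (72 h) and shoulder pain (72 h). Two things differ. The protocol says anesthesia is longer but does not say that nausea or pain becomes more frequent. And every subject has both the research protocol and the implant, so with no standard-CRT group a recorded rate would be a total, not an excess. Femoral bruising is different because its location identifies the source without a comparator. The point is therefore limited to bruising.

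**The case against.** The strongest reply is that this is a disclosed exception, limited in time and severity, to a general rule. Section 12.1 sets the all-events rule and the exemption in the same paragraph, and SAP 7.10 refers to Section 12. That stands. A reader might infer that the plan contradicts itself about collecting all adverse events. It does not: the events are to be reported as the protocol provides, and the protocol states the exception. What remains is that SAP 7.10 does not repeat the exception, so a reader of its tables would not know that a class of events had been left out.

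A second reply is that an investigator may judge that femoral bruising is not expected in all subjects, and report it. Section 12.1 is worded as permission not to report. This also stands in part, and it means the loss would not be total. But Table 10 calls these events not reportable, the bruising line covers the site, and reporting would then vary with each investigator's reading.

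A third reply is that the protocol links bruising to heparin, not to femoral access. That is correct. The link to the access site is an inference from the arterial puncture in Section 10.6.1.

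Finally, the Table 10 cell is broken in the available text, and the text of the ancillary adverse event objective is not shown. Neither can be held against the plan, and either might qualify the point.

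**Conclusion.** The point holds in a narrow form. As worded, the exemption lets early, non-worsening, mild to moderate bruising at the femoral access site go unreported, although that site exists only for the research catheter. It would then be missing from the SAP 7.10 summaries.

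The size is modest and cannot be put as a number. Enrolment is up to 60, but no bruising rate is given, so any count of missed subjects would rest on an assumed rate. No primary or secondary objective is affected.

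A reader might go further and infer that the safety report will show no study-added groin harm in the first week. The documents do not support this: the more serious access-site events are outside the exempt list and reportable from the start, and so is bruising that worsens. Nor do they support extending the point to nausea or to back and shoulder pain, for the reasons in step 6 of the working.

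The conclusion assumes that the routine implant in these subjects uses no femoral arterial access and that sites follow Table 10 as worded. This is a cheap improvement in safety ascertainment, not a flaw that threatens the study.

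**What to change.** Limit the bruising line in Table 10 to the device pocket and incision, matching the pain line. Femoral access-site bruising then becomes a reportable adverse event from the time of the procedure. Add one sentence to SAP 7.10 saying that the remaining unavoidable events, within their windows, are excluded from the adverse event summaries.

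No new SAP table is needed. Bleeding needs no change because it is not exempt. Items for nausea or for back and shoulder pain are not worth adding, since without a standard-CRT comparator they could not show an excess.

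The cost is the change in wording, a note in site training, some extra forms for minor events and a slightly less favourable event count.

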#### Medtronic

Form

### 12.5 Reporting of Adverse Events and Device Deficiencies

Timely, accurate, and complete reporting and analysis of safety information for clinical studies are crucial for the protection of subjects. Reporting and analysis of safety data are mandated by regulatory authorities worldwide. Medtronic has established procedures in conformity with worldwide regulatory requirements to ensure appropriate reporting of safety information. This study will be conducted in accordance with these procedures and regulations.

Adverse Event and Device Deficiency data collection starts once the subject is consented and continues throughout the study, and updates are expected when there are changes in status of a previously reported adverse event including change in actions taken, change in outcome, or change in relatedness. If applicable, these AEs and DDs will be reported to other countries where studies are conducted with the same or a similar product.

### 12.5.1 Adverse Event and Device Deficiency Collection

### 12.5.1.1 Adverse Events

Reporting of AEs to Medtronic will occur on an Adverse Event eCRF, including a description of the event, the diagnosis, the date of event onset, the date the site became aware of the event, the relatedness and seriousness of the event, diagnostic tests and procedures performed, actions taken as a result of the event, and outcome of the event. Each AE must be recorded on a separate AE eCRF. Subject deaths are also required to be reported and should be collected on an AE CRF with a Fatal outcome. Refer to section 12.6.1 for subject death collection and reporting requirements. In addition, AEs impacting users or other persons will be collected on a Non-subject Adverse Event eCRF.

Documented pre-existing conditions are not considered AEs unless the nature or severity of the condition has worsened post implant. In all geographies, unavoidable adverse events, listed in Table 10, need not be reported unless the adverse event worsens or is present outside the stated timeframe.

For any changes in status of a previously reported AE (i.e., change in actions taken, change in outcome, change in relatedness), an update to the original AE must be provided. All reported adverse events must be followed until the adverse event has been resolved, the subject exits the study or until study closure, whichever occurs first. At the time of study exit, all collected AEs with an outcome of "not recovered/not resolved", "recovering/resolving" or "unknown" must be reviewed and updates provided as applicable.

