#### **10.4 Enrollment**

A subject is considered enrolled when the consent process has been finalized. The date the subject signed the IC and Data Protection Authorization, as required by law, must be documented in the subject's medical records. A log of all subjects enrolled in the study should be maintained. Enrollment can be a stand-alone visit or can occur on the same day as the baseline visit. Once consent is obtained, report adverse events/deaths, study deviations and subject exits as they occur.

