## 10.5 Baseline

Following subject enrollment, a baseline visit will be performed within 30 days. The baseline visit can be a standalone visit or occur on the same day as enrollment. The following procedures/data collection will be conducted during the baseline visit:

- Inclusion/exclusion criteria assessment
- Demographics
- Medical History
- Physical Exam

Version 4.0, 29-Apr-2022

Page 35 of 88

Medtronic

Form

- Medication Assessment
- Baseline 12-Lead ECG (within 60 days prior to enrollment)
- Baseline Echocardiography including LVEF and LVESV (within 60 days prior to enrollment)
- NYHA classification
- Adverse events (as applicable)
- Hospitalizations (as applicable)
- Death (as applicable)
- Study Deviations (as applicable)

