### 10.11 Assessment of Safety

AE information is collected in this study. See Section 12 for further information on the collection of AEs and safety information.

All AEs will be collected throughout the duration of a subject's participation in the study, beginning at the time of informed consent. Additionally, any device deficiencies related to the Medtronic CRT-D/CRT-P will be collected. Adverse events and device deficiencies will be reported to Medtronic via completion of eCRFs. See section 12 for additional details.

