# 12.4 Definitions/Classifications

Adverse event (AE) and device deficiency (DD) ISO 14155:2020 definitions are provided in Table 10 below. Where the definition indicates "device", it refers to any device used in the study. This might be the device under investigation, or any market released component of the system. Where the US and ISO terminology differs, the US term is listed first, followed by the ISO term.

Ge	eneral
Adverse Event (AE)	Untoward medical occurrence, unintended disease or injury, or untoward clinical signs (including abnormal laboratory findings) in subjects, users or other persons, whether or not related to the investigational medical device and whether anticipated or unanticipated. NOTE 1: This definition includes events related to the investigational medical device or the comparator. NOTE 2: This definition includes events related to the procedures involved. NOTE 3: For users or other persons, this definition is restricted to events related to investigational medical devices or comparators. (ISO 14155:2020, 3.2)

 Table 10: Adverse Event and Device Deficiency Definitions

CSPOT (Conduction System Pacing Optimiz Therapy) Clinical Investigation Plan	zed		Form
Version 4.0, 29-Apr-2022	Page 52 of 88		Medtronic
Adverse Device Effect (ADE)	lated to the use of an	investio	ational

Adverse Device Effect (ADE)	Adverse event related to the use of an investigational medical device.
	NOTE 1: This definition includes adverse events resulting from insufficient or inadequate instructions for use, deployment, implantation, installation, or operation, or any malfunction of the investigational medical device.
	NOTE 2: This definition includes any event resulting from an error use or from intentional misuse of the investigational medical device.
	NOTE 3: this includes 'comparator' if the comparator is a medical device
	(ISO 14155:2020, 3.1)
Device Deficiency (DD)	Inadequacy of a medical device with respect to its identity, quality, durability, reliability, safety or performance.
	NOTE 1: Device deficiencies include malfunctions, use errors and inadequate in the information supplied by the manufacturer including labeling.
	NOTE 2: This definition includes device deficiencies related to the investigational medical device or the comparator.
	(ISO 14155:2020, 3.19)
I	Relatedness
CRT-D/CRT-P Procedure Related	An adverse event that occurs that is directly related to the insertion or modification of the CRT-P/CRT-D system.

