7.10 Safety Evaluation

See Section 12 of CIP

All adverse events will be collected throughout the study duration, starting at the time of signing the ICF. For purposes of reporting, events shall be captured on an AE eCRF. In addition, AEs impacting users or other persons will be collected on a Non-subject Adverse Event eCRF.

The study will utilize an Independent Clinical Events Committee (CEC) to adjudicate a subset of all the adverse events collected in the study for an unbiased assessed of those related to the device or system. At regular intervals, an independent CEC will conduct a medical review at a minimum all CRT-D/CRT-P system and procedure-related adverse events, all CSPOT system related, cardiovascular related AEs, all SAEs and all AEs with a fatal outcome of participants in the study.

If the investigator does not agree with the CEC's adjudication classification, both determinations will be provided within the final report; however, the CEC's adjudication will be used for data analysis. The disagreement will also be included in reporting to ECs and regulatory authorities, if required.

Results will be summarized using descriptive statistics. Number of events, number and percentages of subjects experiencing system and/or procedure-related adverse events will be reported, as well as, in the case of system-related events, the specific component of the system to which the event was related to describe adverse device effects. The seriousness of adverse events and type of event (complication/observation) will also be summarized as well as whether events were unanticipated adverse device effects or unanticipated serious adverse device effects. Details of individual adverse events including MedDRA key term, actions, outcome, relatedness and seriousness will be listed.

The prevalence of adverse events will further be summarized by MedDRA (Medical Dictionary for Regulatory Activities) key term. The Preferred Term (PT) term will be used. The number of events

CSPOT Statistical Analysis Plan	Form
Revision 2.0 Page 28 of 31	Medtronic

and the number of subjects and the percentage of subjects with an event will be summarized per each PT Term.

A listing of deaths will be provided with cardiac relatedness (cardiac death, sudden cardiac-death, etc). All subject deaths must be reported by the investigator to Medtronic on an AE eCRF (AE with fatal outcome).

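### Worsening of a documented pre-existing condition counts as an adverse event only after implant, although adverse event collection starts at consent

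*Protocol*

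**What the plan says.** The rule at issue is in protocol section 12.5.1.1: "Documented pre-existing conditions are not considered AEs unless the nature or severity of the condition has worsened post implant".

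The other passages on when collection starts name consent, and none makes an exception for pre-existing conditions:

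- Protocol 10.4: "Once consent is obtained, report adverse events/deaths, study deviations and subject exits as they occur".
- Protocol 10.11: "All AEs will be collected throughout the duration of a subject's participation in the study, beginning at the time of informed consent".
- Protocol 12.5: "Adverse Event and Device Deficiency data collection starts once the subject is consented".
- SAP 7.10: "All adverse events will be collected throughout the study duration, starting at the time of signing the ICF".

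Protocol 10.5 lists AEs and hospitalizations among the data for the baseline visit, which comes before any implant. Table 10 in section 12.4 defines an AE as "Untoward medical occurrence, unintended disease or injury, or untoward clinical signs (including abnormal laboratory findings) in subjects, users or other persons", with no start point tied to implant.

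On the separate label question, Note 1 under Observation in Table 10 confines the sponsor's and the clinical events committee's (CEC's) choice between complication and observation to cardiovascular and heart failure related AEs. Table 11 asks the same two parties for that label on every AE related to the system or a procedure. SAP 7.10 plans to summarize the label and names no scope.

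**The concern.** Sections 12.5 and 12.5.1.1 are adjacent and give a site two different rules. If a subject's known condition worsens after consent but before the procedure, 12.5 calls for an AE record and 12.5.1.1 says that the worsening is not an AE. The study population is indicated for CRT, so heart failure is the pre-existing condition to expect, and its severity can change within weeks.

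What is at stake is the completeness of the safety dataset. SAP 7.10 describes tables and listings of all AEs from the signing of consent. If 12.5.1.1 is followed, those tables omit one class of event for part of the follow-up, and the report would not show it. If some sites follow 12.5.1.1 and others follow 10.4, 10.11 or 12.5, counts by MedDRA term can differ between sites because of wording rather than patients. An event that is not an AE is also not on the direct route to serious AE reporting or CEC review.

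**Working it through.** No figure in the plan depends on this rule. The check is a comparison of texts, followed by the length of the interval.

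**Step 1. What is left out on every reading.** Enrollment is the completed consent (10.4), and implant follows within 30 days (10.6). Worsening after consent and before the procedure starts cannot be post implant, whether 'implant' means the procedure or the device. A subject who leaves before the procedure has no qualifying period at all; section 10.7.4 foresees withdrawal even before the baseline visit.

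**Step 2. What depends on the meaning of 'implant'.**

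- *Whole procedure.* Section 10.6 treats implant as a visit that includes lead placement and the acute protocol. Section 12.1 times unavoidable events from implant, and Table 10 times the same events from the surgical procedure. Section 14.4 describes the acute measurements as taken at implant. SAP 7.1.3 uses the word for the leads. On this reading, only the interval from consent to procedure is left out.
- *Device only.* Sections 10.6.1 and 10.6.2 place the acute protocol before the device is implanted. On this reading, worsening during lead placement and the acute protocol is also left out, as is any worsening in a subject with an implant attempt but no device, which section 10.7.2 lists as an exit reason.

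**Step 3. Length of the interval.** Inputs from the visit table in section 10.7: implant at d = 0, 15 or 30 days after enrollment (open, target, close), and the 6-month visit at f = 150, 180 or 210 days after implant. Section 14 allows up to 60 subjects. The share of time in study before implant is d / (d + f), assuming that all 60 enroll and complete:

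- Same-day consent and implant: d = 0, share 0.
- Target days: 15 / (15 + 180) = 7.7%, or 60 × 15 = 900 of 60 × 195 = 11,700 subject-days.
- Latest implant, target visit: 30 / (30 + 180) = 14.3%.
- Latest implant, latest visit: 30 / (30 + 210) = 12.5%.
- Latest implant, earliest visit: 30 / (30 + 150) = 16.7%, or 1,800 of 10,800 subject-days, the largest share within the windows.

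These are shares of calendar time. They say nothing about how many events occur in that time, and the documents give no rate from which to work that out.

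**Step 4. What is still recorded.** New-onset events before implant are AEs under every passage. Deaths go on an AE form (12.6). Hospitalizations are collected as they occur (Table 6, 10.5, 10.6), so a worsening that leads to admission leaves a hospitalization record. What is lost entirely is worsening without admission.

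**Step 5. Which outputs can change.** Before the procedure, no lead, catheter, ECG Belt or device has been used, so worsening then cannot be system or procedure related as Table 10 defines those terms. The outputs open to change are the all-AE tables and the listings by MedDRA term. SDAT and LV dP/dt max are measured during the procedure, and LVEF and LVESV come from echocardiography. The Clinical Composite Score uses heart failure events, but it is meant to describe the response to CSPOT pacing, which begins after implant.

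**Step 6. The label.** A non-cardiovascular, system-related AE falls only under Table 11. An unrelated cardiovascular AE falls only under Table 10. Neither scope contains the other, and Note 1 says that its scope is the only one, so the two cannot both be followed.

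**The case against.** The best defense is that 12.5.1.1 is a deliberate, narrower exception to a general rule. Events before the procedure cannot bear on the safety of the system, so leaving out background fluctuation keeps noise out of the tables. Three further points support this. First, the rule covers only documented conditions, and section 10.7 gives baseline, where medical history is taken, the same 0/15/30-day window as implant; if documentation means that visit, the interval from documentation to implant is zero at the target days. Second, the AE forms and their guidance are under separate cover and sites are trained on them, so one rule may already apply in practice. Third, the note to the serious AE definition excludes planned admissions for a pre-existing condition only where health has not seriously deteriorated, which suggests that serious deterioration is meant to count at any time.

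Much of this stands. The point about relatedness is right and limits the importance. Divergence between sites is possible, not shown. The window point can shorten the interval, although it lapses if earlier records count as documentation.

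What does not stand is the claim of a stated exception. The protocol gives no reason for one, and 10.4, 10.11, 12.5 and SAP 7.10 mention none. If one is intended, SAP 7.10 describes a dataset that the protocol does not collect. The serious AE note does not settle the matter, since a serious AE must first be an AE.

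A reader might also infer that events caused by the leads, the pressure catheter or the acute protocol go uncounted. The documents do not support that as a general conclusion. It needs the device-only meaning of 'implant', which several sections contradict, and even then it concerns only worsening of known conditions.

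**Conclusion.** The contradiction is real and is wrong as written, but its reach is narrow. The part that rests on no interpretation is worsening of documented conditions between consent and procedure: 0 to 30 days per subject, 15 at target, none with same-day implant. The effect is possible incompleteness, and possible inconsistency between sites, in the all-AE tables and MedDRA listings.

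An effect on system or procedure related counts is conditional on the device-only meaning of 'implant'. The percentages above are ceilings on calendar exposure, assume full enrollment and follow-up, and should not be read as a rate of undercounting. The number of affected events cannot be derived. No primary or secondary efficacy estimate changes.

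The label conflict is separate and minor. No AE is lost, and the direction of any difference cannot be determined. Protocol section 14.6 and the detail of SAP 7.9 are not shown in the public copy and might state a scope, but the two tables disagree as printed.

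**What to change.** In protocol 12.5.1.1, count worsening of a documented pre-existing condition from informed consent instead of from implant, and use the same wording in the AE form guidance. This restores the start point already given in 10.4, 10.11, 12.5 and SAP 7.10, and it removes the ambiguity about the acute protocol. For subjects already enrolled, either retrieve such events from the records or state the change of rule in the report.

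The cost is one phrase in the protocol, the matching form guidance and a few more AE forms. Some of those will describe natural fluctuation before the procedure, which the relatedness field has to separate.

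For the label, reconcile Table 10 Note 1 and Table 11 to one scope and name it in SAP 7.10. Either table's scope or the union of both would do. The cost is one table entry and one sentence.
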